## Duration of study – justification

The time course of adaptations in muscle strength, mass and function is complex. During the first weeks of strength training, the brain responds to training by recruiting more motor units with each muscle contraction. This increases the force you can generate. It also increases how rapidly these motor units fire, this is called neuromuscular adaptation. After 4 to 6 weeks of training, if the muscles have been challenged sufficiently, the muscle fibres will start to increase in size, this causes a greater increase in muscle strength as the muscle cross-sectional area enlarges or "hypertrophies".

Previous research studies (Dibble et al. 2006; Alkner, et al., 2004; Frontera, et al., 1988; Fiatarone, et al., 1990; Grimby, et al., 1985) using resistance exercise show a varied duration. Most commonly studies of between 10-12 weeks are performed. The S-Press research study will perform resistance exercises for a 6-week period. This is the amount of time that the patients are in-patients on the ward and gives enough time to observe changes in strength and muscle fibres over this time.

The study will be completed by June 2022.

Short title: S-Press

Sponsor code: JT Rehab-01

IRAS number: 251647

#### **Criteria for participant selection:**

### 1 - NHS in-patients – quantitative and qualitative arms of the study

#### Inclusion criteria:

 Any in-patient admitted onto the ward sites for therapy intervention, assessed as medically stable and physically able to participate by nursing staff and able to provide informed written consent for participation.

The implications of joining the study will be discussed with the participant to ensure full understanding. Written documentation with explanation of study will be left with participant for relatives/carers information.

#### **Exclusion criteria:**

- Any patient who is unable to give informed consent.
- Significantly confused patients may not understand or retain the information to perform the exercises so will be excluded from this study.
- Patients with unstable or deteriorating medical conditions or are acutely unwell with an infection.
- Patients unable to do leg press exercise
- Patients who have had major surgery or myocardial infarction within the past 6 months.
- Patients who have major surgery scheduled during the intervention period.
- Patients currently undergoing treatment for cancer
- Patients who currently have high blood pressure that is uncontrolled (Systolic >200mmHg or Diastolic > 110mmHg)
- Patients with a physical disability that precludes safe and adequate testing.
- Patients with acute pulmonary embolism, infarction, or deep venous thrombosis.

Short title: S-Press

Sponsor code: JT Rehab-01

IRAS number: 251647

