### Criteria for participant withdrawal

Participants (both NHS staff and in-patients) may voluntarily withdraw from the study at any point. Participants will be informed that their participation is voluntary and that they may withdraw from the study at any time without giving a reason and without it affecting their clinical care or legal rights. Any data provided to that point will be used unless the patient requests otherwise. If the patient requests to have their data withdrawn, all data relating to that participant will be securely destroyed. From a clinical perspective, any in-patient participant that experiences an adverse event will be removed from the study. During exercise sessions, heart rate and blood pressure will be monitored, and where necessary sessions ceased. For blood pressure measures, exercise sessions will be stopped a systolic blood pressure measurement of >210mmHg for men and >190mmHg for women or a decrease of systolic blood pressure >10mmHg from resting values will be considered as stop points (American College of Sports Medicine, Guidelines for exercise testing and prescription, 10th Edition). The occurrence of such event will be classed as criteria for withdrawal from the study on safety grounds.

There is a very small chance of joint injury around the knee or an increase in pain associated with osteoarthritic joints. Knee injury risk will be reduced by the supervision of sessions and individualised set up of the S-Press device. A significant increase in joint pain resulting from using the device will be a withdrawal criterion.

Short title: S-Press

Sponsor code: JT Rehab-01

IRAS number: 251647

Should participant withdrawal occur, this will be followed-up by the chief investigator and documented with the study findings.

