#### **Exercise Sessions**

First, participants will be asked to warm up supervised by the physiotherapist, this will incorporate some low intensity range of movement exercise and light stretching.

Staff participants will set up the patient participant using the S-Press protocol for set up. Patients can remain on the bed or in the chair so will not require transferring or position change by the staff for use.

Short title: S-Press

Sponsor code: JT Rehab-01

IRAS number: 251647

Initial assessment of appropriate resistance level will be examined at the beginning of the first session, by assessing the patient participants 1 repetition max (1RM) level (maximum resistance level ability - Instructions stated in set up protocol).

Participants will then complete 3 sets of 10 repetitions on each leg firstly for the knee extensors and then the knee flexors. The S-Press allows both Concentric and Eccentric muscle actions, so muscle groups are performed independently. A guide of 1 minute's rest will be provided in between sets and legs, although more rest will be allowed if required by the participants. The amount of time per exercise session will be approximately 30 minutes.

Blood pressure and heart rate will be measured before the exercise session begins, mi-way through and again at the end of the session. This is to ensure that there is maintenance of optimal levels of blood pressure and heart rate and monitoring of any adverse effects. These measurements are regularly taken by therapy staff to assess their patients' conditions before and during physical intervention.

Data from the assessments will be analysed using paired t-tests. As this trial is an efficacy and feasibility trial descriptive statistics (mean, standard deviation and % Change) will be calculated. In addition, Cohen's D will be used to determine effect sizes to quantify the magnitude of any differences in variables. A p value of p<0.05 will be used to determine significance, with effect size of <0.2=small; 0.5= moderate; >0.8 large.

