#### **Serious adverse event reporting:**

Potential adverse events that are common to novel physical activity such as delayed muscle soreness, feeling faint as well as temporary increases in heart rate, breathing rate and blood pressures, are planned for within the study and risk minimized with a thorough warm up and cool down with participants as well as supervision throughout the session.

There is a very small chance of joint injury around the knee or an increase in pain associated with osteoarthritic joints. Knee injury risk will be reduced by the supervision of sessions and individualised set up of the S-Press device. A significant increase in joint pain resulting from using the device will be a withdrawal criterion.

Although there is a risk associated with physical activity, numerous studies have shown that physical activity is safe, and beneficial to the health of patients in this environment (Henskens et al., 2018; Kalinowski et al., 2012). The most severe risks associated with physical activity are death or serious cardiac event (Vuori 1986).

Increasing or maintaining skeletal muscle mass has also been shown to increase quality of life and reduce the incidence of MSK injuries caused by trips and falls (Skelton & Beyer 2003).

Participants will be made aware of all the processes involved in data collection stages before the beginning of the study. Individual clinicians will be aware of their medical history and will have upto-date training on first aid and dealing with any adverse events that could potentially occur.

Individual sessions will be postponed or cancelled if an individual is feeling unwell. If the session has started and participants suddenly feel ill whilst performing exercises or they experience tissue viability issues to do with skin integrity or damage caused by the S-Press or signs of cardiac event, then nursing staff will be alerted and session ended. Any adverse event, serious or not will be reported back to nursing staff and reported with the daily log and data collection sheets.

Data will be collected in line with the NIHR guidance on good clinical practice. The PI will ensure the study is carried out in accordance with the protocol (equipment calibrated, facilities suitable and

Short title: S-Press

Sponsor code: JT Rehab-01

IRAS number: 251647

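### Women may enter with a resting systolic pressure up to 200 mmHg, but exercise stops, with withdrawal, above 190 mmHg

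*Protocol*

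**What the plan says.** Three parts of the Protocol bear on this.

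- **Entry.** Under Exclusion criteria, the only numerical blood-pressure limit is "Patients who currently have high blood pressure that is uncontrolled (Systolic >200mmHg or Diastolic > 110mmHg". It is the same for men and women, so a systolic value of exactly 200 mmHg is eligible. The inclusion criteria do not restrict sex.
- **Stopping and withdrawal.** Criteria for participant withdrawal opens the rule with "During exercise sessions, heart rate and blood pressure will be monitored, and where necessary sessions ceased". The stop points are "a systolic blood pressure measurement of >210mmHg for men and >190mmHg for women or a decrease of systolic blood pressure >10mmHg from resting values", and the consequence is that "The occurrence of such event will be classed as criteria for withdrawal from the study on safety grounds".
- **Timing of readings.** Exercise Sessions states: "Blood pressure and heart rate will be measured before the exercise session begins, mi-way through and again at the end of the session". The same section has the starting resistance "examined at the beginning of the first session, by assessing the patient participants 1 repetition max (1RM) level".

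On the expected direction of change, the section on serious adverse event reporting says that "temporary increases in heart rate, breathing rate and blood pressures, are planned for within the study".

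**The concern.** An entry limit should sit at or below the level at which the same protocol judges exercise unsafe. For men it does. For women the order is reversed, so the Protocol admits women whose resting pressure already exceeds their own stop point.

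What happens next depends on a point the Protocol leaves open. The stop rule refers to readings during exercise sessions, and it is unclear whether the reading taken before the session counts.

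- If it counts, an eligible woman in this range cannot start and meets a withdrawal criterion without having used the device.
- If it does not count, no stated blood-pressure rule prevents her from starting. In the first session the one-repetition-maximum test then comes before the next scheduled reading, so she makes a maximal effort while already above her stop point.

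Safety of the device is one of the primary objectives. A withdrawal on safety grounds in such a woman would largely reflect the entry rule, yet it would be reported as a safety event in a study of the device.

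**Working it through.** **Inputs, all from the Protocol**

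| Quantity | Men | Women | Section |
|---|---|---|---|
| Highest eligible resting systolic (mmHg) | 200 | 200 | Exclusion criteria |
| Upper stop point: systolic above (mmHg) | 210 | 190 | Criteria for participant withdrawal |
| Lower stop point: fall from rest of more than (mmHg) | 10 | 10 | Criteria for participant withdrawal |

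**Step 1: headroom (stop point minus entry limit)**

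- Men: 210 − 200 = +10 mmHg.
- Women: 190 − 200 = −10 mmHg.

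The overlap for women is the ten whole-mmHg resting values 191 to 200. For men there is none.

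**Step 2: readings that trigger neither rule**

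For resting systolic S, a woman's safe readings run from S − 10 to 190. The count is 190 − (S − 10) + 1 = 201 − S. The smallest fall that brings her to 190 is S − 190.

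| Participant | S | Safe readings | Count | Change needed |
|---|---|---|---|---|
| Woman | 191 | 181 to 190 | 10 | fall of 1 to 10 |
| Woman | 195 | 185 to 190 | 6 | fall of 5 to 10 |
| Woman | 200 | 190 only | 1 | fall of exactly 10 |
| Man | 200 | 190 to 210 | 21 | anything from −10 to +10 |

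Every woman in the overlap must show a fall during exercise to stay in the study, while the Protocol expects a rise. The second stop rule closes most of the remaining escape.

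**Step 3: how likely is a trigger?**

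The Protocol gives no distribution of blood-pressure change, so this step rests on an assumption. Take the change from rest to one in-session reading as normal with mean μ and standard deviation σ, rounded to whole mmHg. Then

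P(trigger) = 1 − [Φ((190.5 − S − μ)/σ) − Φ((−10.5 − μ)/σ)].

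For example, with S = 191, μ = 0 and σ = 8, the bracket is Φ(−0.0625) − Φ(−1.3125), about 0.38, so P is about 0.62.

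| Assumed mean rise (σ from 8 to 12) | S = 191 | S = 195 | S = 200 |
|---|---|---|---|
| 0 mmHg | 62–71% | 81–84% | 98% |
| 10 mmHg | 85–91% | 93–97% | over 99% |
| 20 mmHg | 96% or more | 98% or more | over 99% |

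These figures are for a single reading. Each session has two readings after the start (mid-way and end), and a second reading can only raise the chance.

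**Step 4: what a lower entry limit would do**

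At S = 190 a woman has 11 safe readings (180 to 190). At S = 180 she has 21 (170 to 190), the same number as a man at 200. Under the same model with σ = 10 and a mean rise of 10 mmHg, a single reading triggers a rule with probability 85% at S = 190, 50% at 180 and 17% at 170.

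**The case against.** The strongest reply is that the overlap may never matter in practice.

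- **Clinical screening.** Nursing staff must judge each patient medically stable and physically able, unstable conditions are excluded, and therapy staff will have the pre-session reading in hand. Few wards would put a woman at 195 mmHg through a maximal test. This makes the worst outcome less plausible, but none of these filters carries a pressure value, and the one criterion that does admits her.
- **Likelihood is inferred.** The Protocol does not say how far pressure rises, and a count of whole-mmHg values is not a probability. This stands: the overlap is certain, whereas the percentages depend on the assumed model. Even with no mean rise, a trigger is more likely than not throughout the range.
- **Data loss is not shown.** The familiarisation session comes before baseline and might identify such a woman before any paired data exist, and the sample size already allows for 20% attrition. This also stands, so loss after baseline is not claimed. However, no blood-pressure check is stated for familiarisation, which includes practice of the exercise itself.
- **The stop rule protects her.** It does once a reading is taken. Exposure before the mid-way reading remains if the pre-session value does not count.
- **The replacement value is a judgement.** Nothing in the Protocol shows that 10 mmHg of headroom is enough, and a limit of 190 leaves no room for any rise. This is right, and the value should be a clinical choice.

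**Conclusion.** The point holds. For women the entry limit lies 10 mmHg above the stop and withdrawal point; for men it lies 10 mmHg below. This follows directly from the stated limits and needs no assumption.

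That an affected woman is very likely to be withdrawn in her first monitored session is an inference. It rests on the rise in pressure that the Protocol expects and on the narrow band of falls that avoids both rules. Under the assumed model, the chance at a single reading is at least 62% with no mean rise and at least 85% with a mean rise of 10 mmHg.

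The number of women concerned is unknown and may be zero. One avoidable withdrawal would be 1/15 = 6.7% to 1/20 = 5% of recruits. At the lower target, 15 × 0.8 = 12 leaves exactly the minimum cited in the sample size section. The case for correction rests mainly on participant safety and on clear attribution of safety withdrawals. It should be corrected before recruitment.

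**What to change.** Two wording edits to the Protocol.

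1. **Exclusion criteria:** give women their own resting systolic limit, no higher than 190 mmHg. A limit of 180 mmHg gives the 10 mmHg headroom that men already have and is preferable to 190, which allows for no rise. The sponsor's clinicians should choose the value.
2. **Criteria for participant withdrawal:** state that a pre-session reading above the limit postpones that session, and that the stop and withdrawal points apply to readings taken during or at the end of exercise. This wording would serve men as well.

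The cost is that women resting at 191 to 200 mmHg (or 181 to 200 if 180 is chosen) become ineligible. Their number is unknown and may be zero. No change to the assessments or the analysis is needed.

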### 2 - NHS Staff - Qualitative arm of the study only

#### Inclusion criteria:

 Any NHS staff delivering therapy care to in-patients (for example: qualified physiotherapists, physiotherapy assistants or technical instructors, trained nurses, clinical support assistants, and activity co-ordinators).

Staff will be trained to set up and deliver the S-Press exercise session with the patients. This should constitute minimal additional work burden as they would be exercising with these patients during their normal 30-minute physio session and will give alternative therapeutic options for treatment sessions.

#### Exclusion criteria:

• Any staff who do not deliver therapy care (for example catering and domestic staff).

### Criteria for participant withdrawal

Participants (both NHS staff and in-patients) may voluntarily withdraw from the study at any point. Participants will be informed that their participation is voluntary and that they may withdraw from the study at any time without giving a reason and without it affecting their clinical care or legal rights. Any data provided to that point will be used unless the patient requests otherwise. If the patient requests to have their data withdrawn, all data relating to that participant will be securely destroyed. From a clinical perspective, any in-patient participant that experiences an adverse event will be removed from the study. During exercise sessions, heart rate and blood pressure will be monitored, and where necessary sessions ceased. For blood pressure measures, exercise sessions will be stopped a systolic blood pressure measurement of >210mmHg for men and >190mmHg for women or a decrease of systolic blood pressure >10mmHg from resting values will be considered as stop points (American College of Sports Medicine, Guidelines for exercise testing and prescription, 10th Edition). The occurrence of such event will be classed as criteria for withdrawal from the study on safety grounds.

There is a very small chance of joint injury around the knee or an increase in pain associated with osteoarthritic joints. Knee injury risk will be reduced by the supervision of sessions and individualised set up of the S-Press device. A significant increase in joint pain resulting from using the device will be a withdrawal criterion.

Short title: S-Press

Sponsor code: JT Rehab-01

IRAS number: 251647

Should participant withdrawal occur, this will be followed-up by the chief investigator and documented with the study findings.

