#### **Research objectives:**

### **Primary Objectives:**

The primary objectives are to quantify changes in the following in response to 12 sessions (2x per week for 6 weeks) of using the S-Press device supervised by a Physiotherapist. The primary outcomes are to assess:

- Functional improvements using the 5x sit to stand test.
- Morphological changes, measuring muscle thickness of the Vastus Lateralis and Rectus Femoris muscle using B-Mode ultrasound.
- Any safety issues with *S-Press* use with older users.
- Perceptions of usability of the S-Press with older adult users and care givers.

Short title: S-Press

Sponsor code: JT Rehab-01

IRAS number: 251647

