### Sample size justification:

For the study we will aim to recruit 15 - 20 NHS in-patient participants across the 4 sites. Sample size aligns with previous research studies using similar methodology (e.g., Dibble et al. 2006; Alkner, et al., 2004; Frontera, et al., 1988; Fiatarone, et al., 1990; Grimby, et al., 1985; Pyka, et al. 1994; Hagerman et al. 2000; Hepple, et al. 1997)

Typical exercise training studies of this length have 10-15 participants per arm of the trial. This would conventionally include a control group. As this is a feasibility trial, the advice from our RDS was that a control group was not required. An N of 12 has been recommended as a minimum number of participants per group to be recruited for a clinical trial where there is no prior information to guide sample size (Julious 2005). This figure is suggested to represent the lower threshold required to estimate the standard deviation of measures with adequate precision. We aim to recruit 15-20 participants to the study to allow for a predicted 20% attrition rate.

This low number of patient participants per site will provide a low burden for the staff participants.

Short title: S-Press

Sponsor code: JT Rehab-01

IRAS number: 251647

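### Destruction of all data on a withdrawn patient's request has no exception for adverse events or exposure, so the primary safety outcome could lose an event together with its denominator

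*Protocol*

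**What the plan says.** All references are to the Protocol.

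- **Criteria for participant withdrawal, default:** "Any data provided to that point will be used unless the patient requests otherwise".
- **Same section, on request:** "If the patient requests to have their data withdrawn, all data relating to that participant will be securely destroyed".
- **Same section, removal after harm:** "any in-patient participant that experiences an adverse event will be removed from the study". A significant rise in joint pain from the device and the blood pressure stop points are also grounds for withdrawal.
- **Same section, last sentence:** "Should participant withdrawal occur, this will be followed-up by the chief investigator and documented with the study findings".
- **Primary Objectives:** the four primary outcomes include "Any safety issues with *S-Press* use with older users".
- **Serious adverse event reporting:** "Any adverse event, serious or not will be reported back to nursing staff and reported with the daily log and data collection sheets".
- **Sample size justification:** "We aim to recruit 15-20 participants to the study to allow for a predicted 20% attrition rate".

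**The concern.** The destruction rule covers all of a patient's data and names no exception. The daily log and data collection sheets are study records, so read literally their adverse event entries for that patient fall under it. Every in-patient with an adverse event is removed from the study. Each patient who counts for the safety outcome therefore also becomes a withdrawn patient, for whom a request may arise.

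Two things are at stake. First, the study has one arm and 15 to 20 patients, and its safety data are meant to support CE marking, so a single record carries much weight. Erasure removes the patient from both the numerator and the count of exposed patients, so a reader of the report might not see that anyone is missing. Second, the section promises without condition that withdrawals will be documented with the findings, and also promises without condition to destroy everything on request. It does not say how the two fit together.

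A statistical analysis plan could not repair this, because it cannot analyse records that no longer exist. Retention has to be settled in the protocol and the participant information before enrolment.

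**Working it through.** **1. The plan's own figure.** The Sample size justification gives a minimum of 12 and predicted attrition of 20%. Inflating, 12 / (1 − 0.20) = 15, the lower end of the stated 15 to 20. The figure is reproduced and is not in dispute. It supplies the range of N used below.

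**2. The rules applied to one patient.** Take an in-patient who has an adverse event and later asks for data to be withdrawn.

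| Section | Rule | Result for this patient |
|---|---|---|
| Serious adverse event reporting | Event reported to nursing staff and entered in the daily log and data sheets | A study record of the event exists |
| Criteria for participant withdrawal | Patient with an adverse event is removed | Patient is withdrawn |
| Same | On request, all data are destroyed | The study record of event and exposure goes |
| Same | Withdrawal is documented with the findings | Some record of the withdrawal is still expected |

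The third and fourth rows pull against each other, and no section ranks them. Without a request, the default of retention applies and no conflict arises.

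**3. Size of one erasure (illustration).** The protocol gives no expected adverse event rate and no rate of destruction requests. Assume that x = 1 to 3 patients have an event and that one of them asks for destruction. The observed proportion then moves from x/N to (x − 1)/(N − 1).

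| N | x | Before | After | Change (points) |
|---|---|---|---|---|
| 15 | 1 | 1/15 = 6.7% | 0/14 = 0% | 6.7 |
| 15 | 2 | 2/15 = 13.3% | 1/14 = 7.1% | 6.2 |
| 15 | 3 | 3/15 = 20.0% | 2/14 = 14.3% | 5.7 |
| 20 | 1 | 1/20 = 5.0% | 0/19 = 0% | 5.0 |
| 20 | 2 | 2/20 = 10.0% | 1/19 = 5.3% | 4.7 |
| 20 | 3 | 3/20 = 15.0% | 2/19 = 10.5% | 4.5 |

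The shift is thus about 4.5 to 6.7 points. Exact (Clopper-Pearson) 95% intervals for the single-event case:

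- N = 15: 0.2% to 31.9% before, 0% to 23.2% after.
- N = 20: 0.1% to 24.9% before, 0% to 17.6% after.

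The intervals are wide either way. What changes in kind is that one observed event becomes none.

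**The case against.** The case on the other side has several parts.

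- **Retention is the default.** Destruction needs a specific request, and no frequency of requests is given. This stands: the loss is possible and may never occur.
- **The sentences need not contradict each other.** A reader might infer that documenting a withdrawal becomes impossible once the data are destroyed. The documents do not support that. The promise is to document the withdrawal, not to keep patient-level data, and an anonymous note that one participant withdrew and asked for removal could arguably satisfy both. What remains is a tension of scope, because the protocol neither provides for such a note nor says which sentence prevails. Such a note would also not preserve the adverse event.
- **Adverse events are not named in the destruction rule.** The sentence follows the text on voluntary withdrawal, and removal for safety comes after it. The inclusion of adverse events is an inference from the word all. It is the natural reading, since no section supplies an exception.
- **The event may survive elsewhere.** It is also reported to nursing staff, and data collection is to follow good clinical practice guidance. The clinical record may outlast a request, but the protocol does not make it the source of the trial's safety result.
- **A direction of bias is not shown.** A reader might infer that harmed patients are more likely to ask for erasure, so that the safety result will be biased toward no issues. No section supports this. Patients with an adverse event are removed by rule, which says nothing about whether they want their data destroyed, and anyone may withdraw without a reason. Only the possibility of selective loss follows from the text.
- **Full erasure is a legitimate choice in favour of participants.** This stands as a cost to be weighed, and the consent material is not available to show what patients are told.

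**Conclusion.** The point holds in a limited form. As written, a request could remove a recorded adverse event and the exposed patient from the study's own record of a primary outcome, and the relation of that rule to the promise to document withdrawals is left open.

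The documents do not allow the frequency to be estimated. If it happens to one patient with an event, and one to three patients have events, the observed proportion falls by about 4.5 to 6.7 percentage points. A fall of 5.0 to 6.7 points applies only when the erased event is the sole one. This rests on three assumptions: that all data includes adverse event entries, that a patient with an event asks for destruction, and that the trial's safety result is taken from the study records.

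The change is worth making before recruitment, because it alters a stated rule at little cost and cannot be made good once records are gone.

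**What to change.** In Criteria for participant withdrawal, limit destruction on request to efficacy measurements, images and interview recordings. State that a minimal de-identified record is kept of exposure to the device, adverse events already recorded, the fact of withdrawal and, where the patient chose to give one, the reason. Align the closing sentence of that section, the recording duty in Serious adverse event reporting and the participant information with this, so that patients know at consent what is kept.

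The cost is wording in the protocol and the participant information. The patient's erasure option becomes modestly narrower, so ethics review must see the change. The sample size, assessments and clinical rules are unaffected.

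### The withdrawal rule removes patients for any adverse event, minor expected ones included, and so loses their 6-week outcomes and later safety observation

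*Protocol*

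**What the plan says.** The Protocol's section on criteria for participant withdrawal states that, from a clinical viewpoint, "any in-patient participant that experiences an adverse event will be removed from the study". It then sets narrower triggers: systolic stop points during exercise (above 210 mmHg for men, above 190 mmHg for women, or a fall of more than 10 mmHg from rest), of which it says "The occurrence of such event will be classed as criteria for withdrawal from the study on safety grounds", and a joint pain criterion.

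The section on serious adverse event reporting opens with "Potential adverse events that are common to novel physical activity such as delayed muscle soreness, feeling faint", adds short-lived rises in pulse, breathing and blood pressure, and says that the study plans for these effects. For feeling unwell it acts on the session: "Individual sessions will be postponed or cancelled if an individual is feeling unwell". It repeats the joint pain rule: "A significant increase in joint pain resulting from using the device will be a withdrawal criterion". On recording it says "Any adverse event, serious or not will be reported back to nursing staff and reported with the daily log and data collection sheets".

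For patients who leave, the withdrawal section adds "Any data provided to that point will be used unless the patient requests otherwise" and "Should participant withdrawal occur, this will be followed-up by the chief investigator and documented with the study findings".

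The assessments take place at baseline and at 6 weeks, the latter 48 to 72 hours after the final session (Physiological Assessments). They are analysed with paired t-tests (Exercise Sessions). Safety is listed among the primary outcomes (Primary Objectives).

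**The concern.** Removal from the study is tied to an unqualified term that the same document applies to effects it expects to be common. Two consequences follow if staff do what the sentence says.

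First, removed patients have no 6-week value. The change in sit to stand and in muscle thickness is then estimated only in those who had no event. In a single-arm study meant to support CE marking, that group is selected on a response to the device itself.

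Second, the study does not learn whether a patient who was sore or faint once could have continued safely, which is a practical question for a device aimed at older in-patients.

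The text also leaves staff at four sites to decide what the sentence was meant to cover, so the same event could remove a patient at one site and not at another.

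**Working it through.** **Scope of the term.** The withdrawal sentence has no qualifier for severity, seriousness or relatedness. The reporting section calls soreness and faintness potential adverse events. Such an effect becomes an adverse event when it occurs, and nothing in the withdrawal section exempts it. The same section uses the term for events whether serious or not.

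**Check against the other triggers.** The joint pain criterion needs pain that is both significant and caused by the device. If any adverse event already removes the patient, lesser or unrelated joint pain does so too, and this criterion adds nothing. The redundancy suggests that a narrower rule was intended, but no narrower rule is written. For blood pressure, explicit stop points are given, so an operative threshold exists there. The open question concerns the other listed effects, chiefly soreness and faintness.

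**Tracing one patient.** Take a patient with a baseline assessment who reports soreness after an early session.
- Under the withdrawal sentence the patient leaves the study.
- The only post-test is at 6 weeks, so change = (6-week value) − (baseline value) cannot be formed, and the patient drops out of the paired t-test. Keeping the earlier data does not help, because baseline alone gives no pair.
- The event is logged and the withdrawal is documented, so the first safety signal is kept. The remaining sessions of the planned 12 do not take place, and no later assessment is specified.

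**What the sample size allows.** Inputs from the sample size justification: minimum 12, attrition 20%, target 15 to 20.
- Required recruitment: 12 / (1 − 0.20) = 15, which reproduces the lower end of the target.
- Losses allowed from all causes while keeping 12: 15 − 12 = 3, or 20 − 12 = 8.

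The Protocol gives no event rate and does not say whether the 20% includes removals for adverse events. As an assumption only, let q be the chance of a removing event per session, independent over 12 sessions. The proportion removed is 1 − (1 − q)^12:
- q = 1%: 1 − 0.99^12 = 11%
- q = 5%: 1 − 0.95^12 = 46%
- q = 10%: 1 − 0.90^12 = 72%

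The rule alone would use up the 20% allowance at q = 1 − 0.80^(1/12) = 1.8%. A range from 11% to 72% shows only that the loss cannot be sized from the document.

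**Entry limit against in-session limit.** The exclusion criteria bar systolic pressure above 200 mmHg for both sexes. For women the in-session limit is 190 mmHg, and 200 − 190 = 10 mmHg of overlap. For men it is 210 mmHg, and 210 − 200 = 10 mmHg of clearance. A woman above 190 and up to 200 mmHg at rest therefore passes the numeric entry limit but lies above her in-session limit.

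**The case against.** The strongest reply is that the literal reading cannot be what was meant. Exercise normally raises pulse and blood pressure, so if every temporary rise removed a patient, almost nobody would remain. A reader might infer that the Protocol does impose this. It does not support that reading: immediately after the blanket sentence it says that sessions are stopped where necessary and gives numeric systolic limits. This part of the objection stands, and the concern is confined to events without a written threshold.

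A reader might also infer that the two sections contradict each other. They can be applied in sequence (end the session, then remove the patient), and the reporting section nowhere says that such patients continue. The fault is undefined scope.

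A third tempting inference is that the study will fall below 12 patients. No event rate supports that, and at 20 recruits 8 losses are tolerable.

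Caution is defensible in a small feasibility study of a new device in older in-patients, and the first event is captured. That stands too, but caution requires ending use of the device and does not require ending observation. How incomplete data are handled may lie in a statistical analysis plan that is not shown, so no fault is found there. Such a plan could not recover an outcome that the Protocol stops the study from collecting.

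On blood pressure, one limit applies at entry and the other during exercise. The check for medical stability may screen the woman out, and whether the pre-session reading counts towards the stop point is not settled. The mismatch is minor.

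**Conclusion.** The point holds as a badly fixed rule and should be corrected. As written, it ties removal from the study to any adverse event, while the same document treats common and minor effects as adverse events. Patients so removed lose their 6-week outcomes and any observation of later tolerance. The conclusion rests on the plain wording of the withdrawal sentence and on removal meaning no 6-week assessment; no sentence provides for one.

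The size of the loss is unknown. The direction of any bias is not established either: it is reasonable to suspect that event-free patients do better, but nothing in the Protocol shows it. Confidence is high on the defect in the text and does not extend to any projected loss. The blood pressure mismatch is a secondary matter of alignment.

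**What to change.** Amend the withdrawal section as follows.

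1. Replace the blanket sentence with a closed set of reasons for permanently ending use of the S-Press: the existing systolic stop points, significant joint pain caused by the device, and a clinically agreed list of serious or device-related events. Other events are logged and managed at session level.
2. State that a patient who stops the device stays in the study for event follow-up and for the planned 6-week sit to stand and ultrasound, where this is safe, the patient is willing and can still be reached. Time these tests from baseline, because the present window of 48 to 72 hours after the final session does not suit someone who stopped early.
3. Set the entry systolic limit for women no higher than 190 mmHg.

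This is a short amendment with no extra patients and no new measurements. It has practical costs. Some post-tests will follow fewer than 12 sessions, so the average change will include partly treated patients. Some patients will be unfit for the sit to stand test. Assessments are planned on the ward and the 6-week period is matched to the in-patient stay, so some patients may have been discharged and would need to be traced.
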